#### **4. Statistical Analysis Plan**

A repeated measures ANOVA will be conducted to examine the impact of different forward estimators on the real-time forward estimation error, which served as the dependent variable. In this analysis, the forward estimator functioned as the intra-subject factor, with multiple measurements taken for each subject across different conditions. Instances of significant differences were further explored using Tukey's Honesty Significant Difference test to conduct detailed comparisons between specific groups. Paired t-tests were used to compare the offline forward estimation error of each adapted forward estimator with the baseline during overground walking. The error served as the dependent variable in these analyses.

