Several leading edge laboratories have studied pattern recognition techniques to improve intent recognition [10]–[13] – including our own previous work – but a significant drawback to these systems are that they are highly user-specific and rely on acquiring large amounts of training data from each subject. Part of this project will focus on developing a user interface that does not need user dependent training data. Voice recognition software previously required users to train the system with their own voice commands and only a relatively small number of people used it. In contrast, state-of-the-art voice recognition software used in cell phones today does not require any user dependent training and is widely adopted. Similarly, intent recognition systems for prostheses must innovate and provide intent recognition systems that require minimal user specific training so that patients will be willing to use them. We propose to do this through novel sensing technology, smarter algorithms, and adapting to each individual user's patterns. We need an innovative approach to achieve an intent recognition system that can be quickly applied to different users without hours of training time or the need for user specific recalibration. A broad goal of this project is to develop signal processing techniques and novel pattern recognition algorithms to enable user-independent intent recognition for powered lower limb prostheses. We will implement a novel adaptation algorithm that will adapt our intention recognition system to new individuals and provide speed-variable prosthetic assistance – eliminating the need to for any user dependent training. These algorithms will be implemented on the Open Source Leg (OSL) powered prosthesis, which was designed by collaborator [name] [14]. A minimum group of ten individuals who use a prosthetic knee and foot in their clinically prescribed prosthesis will be trained on the powered leg and will complete the experiment. We will compare the accuracy of the intent recognition systems in walking speed estimation and also measure other clinically meaningful parameters including self-selected walking speed and relevant biomechanics. We expect adapted systems to exhibit advantages in walking speed estimation error compared to non-adapted systems and provide appropriate powered response for each walking speed during treadmill and overground walking.

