## **2. Participant population**

Subjects must fit into one of two categories stated in the study design section: able bodied individuals, and disabled individuals/amputees. Disabled individuals are considered

part of a vulnerable population. This group will be protected through the use of safety equipment such as hand rails and a safety harness for the case of stumbles and falls. The goal is to collect data from at least 10-15 participants from the amputee population.

Participants will be between 18-75 years old. Inclusion criteria includes subjects must be between 18-75 years of age, use a prosthetic knee and foot in their clinically prescribed prosthesis (except for the able bodied subjects). Subjects must be at K3 or K4 ambulatory level according to the Medicare/Medicaid designation as the study requires subjects to walk, ascend/descent stairs and ascend/descend ramps. Subjects will be excluded if they have any history of a neurological injury, gait pathology, or a cardiovascular condition that would limit their ability to ambulate for multiple hours during the experimental sessions. Pregnant subjects will also be excluded to the risk of a fall during the experiment.

All participants that meet the appropriate criteria will be recruited through official flyers and verbal scripts, even if they are already known to the researchers. Flyers will be posted around the campus of Georgia Institute of Technology, in designated advertising areas. Additionally, word of mouth recruiting will use a script with similar language as the flyers. Recruiting materials are attached as separate documents including a flyer and e-mail script. Permission will be obtained from participants before using any information for research purposes that has individual identifiers attached.

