### **3. Study Procedures**

This will be a single-visit study. If participants are not able to complete the study during their first visit, they will be asked to return. All testing will take place at the Georgia Tech Manufacturing Institute (GTMI) at the Georgia Institute of Technology. Testing will last between 2-3 hours with no more than 30 minutes of continuous movement and visits will be scheduled at the convenience of the participants.

Able bodied individuals may be fitted with a commercialized assistive walking device, iWALK (user manual attached as separate document), that has been adapted in order to be used with the prosthetic device. This is to ensure controllers are functioning before a subject comes in and walks on the prosthetic device. During all testing participants are instructed to vocalize any concerns or discomfort to researchers. At any time if participants are uncomfortable, they have the right to quit the study with no penalty. The first visit will last no longer than 4 hours. If the participant obliges, they will be asked to return for additional visits, scheduled at their convenience. During additional visits, human participants will be asked to perform typical tasks such as standing, sitting, or walking, in a safe and monitored environment. Tests will begin on a treadmill with a security harness and or gait belt, based on the level of comfort of the participant. If the participant feels comfortable, testing will be moved from the treadmill to the floor for supported and then freestanding walking. Another type of treadmill is a force-instrumented treadmill incorporated into the Computer Assisted Rehabilitation Environment (CAREN). This treadmill is embedded in a large platform that is able to move in six degrees of freedom, allowing the application of disturbances during standing or walking by moving the platform. During all types of testing in which subjects are asked to respond to environmental disturbances, they will be required to wear a safety harness. During tests, verbal feedback

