In order to also measure functional clinical measures, a Protokinetics gait mat will be utilized to measure common measures such as step length, step time, and symmetry. This system is just a mat that users will need to walk on top similar to walking overground. Users will be in a harness and have the options for handrails or gait belt if needed.

Throughout the tests there will be a camera recording the session. The purpose of the camera is to record performance for future analysis. The participant will always have the right to stop the test and/or take a break. The participant may also choose to discontinue participation at any time.

This study will ask participants to walk on treadmill and overground settings to adapt pre-trained (baseline) walking speed estimation machine learning (ML) models to user-specific data. The adaptation pipeline self-labels and updates models with user data in real-time. We explore two methods of self-labeling referred to as Direct Integration (DI) and Ground Truth (GT). DI computes walking speed labels using heel-to-heel foot

displacements measured by a foot inertial measurement unit (IMU). GT provides labels that are the true treadmill speed (for treadmill trials) or center-of-mass speed (for overground trials). Treadmill speed profiles follow either a staircase profile (P1) or a triangular profile (P2). Overground walking is constrained to a 5-meter straight path between two cones. Adapted models are renamed based on the environment (P1, P2, or OVG) and labeling method (DI or GT) used. Models are evaluated on how well they can estimate the current speed (forward estimation). Additionally, we provide biomimetic assistance that scales with estimated walking speed.

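### In its usual complete-row form, the planned repeated measures ANOVA drops any participant who lacks one estimator value; a participant-plus-estimator model on all available data avoids this at little cost

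*Combined protocol and SAP*

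**What the plan says.** Section 4 (Statistical Analysis Plan) is a single paragraph. For the real-time outcome it states: "A repeated measures ANOVA will be conducted to examine the impact of different forward estimators on the real-time forward estimation error". Forward estimator is the within-subject factor, "with multiple measurements taken for each subject across different conditions". Tukey comparisons follow a significant result. Separate paired t-tests compare each adapted estimator with baseline on offline overground error. The section does not list the estimators in the ANOVA, define an analysis set, say how several measurements become one value, or say what happens to a participant with some estimators missing.

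Section 3 (Study Procedures) bears on completeness in four places:
- On unfinished visits: "If participants are not able to complete the study during their first visit, they will be asked to return".
- On stopping: "The participant may also choose to discontinue participation at any time".
- On floor walking: "If the participant feels comfortable, testing will be moved from the treadmill to the floor for supported and then freestanding walking".
- On the estimators: "Adapted models are renamed based on the environment (P1, P2, or OVG) and labeling method (DI or GT) used".

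On numbers, Section 1 describes at least ten prosthesis users who "will be trained on the powered leg and will complete the experiment", and Section 2 says: "The goal is to collect data from at least 10-15 participants from the amputee population".

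**The concern.** A classical repeated measures ANOVA works on complete rows, with one value for every estimator from every participant. If one value is missing, standard routines either drop the whole person or refuse the data as unbalanced. The plan does not say which form of the analysis is meant or what happens to partial records, so the software default would decide.

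Two things are at stake. The first is precision, in a study whose stated minimum is ten people. The second is selection: those who stop early or do not reach the floor may be those who tire or walk less comfortably on the device, and an analysis of completers leaves them out. The floor-walking route matters for this ANOVA only if an estimator adapted overground is one of its levels, which the plan does not state.

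**Working it through.** The documents contain no power calculation to reproduce, so the check asks what incomplete participants would cost.

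**Inputs**
- Participants: n = 10, the minimum in Section 1.
- Estimators: Section 3 allows baseline plus 3 environments x 2 labelling methods, so at most k = 1 + 6 = 7. The number in the ANOVA is not stated. Power is shown for k = 5 and 7, and participant loss for k = 3 to 7.
- Assumed, because the documents give none of these: alpha 0.05; every adapted estimator differs from baseline by 1.25 within-participant residual SDs; independent residuals; participant SD equal to residual SD; all missingness rates.

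**Step 1. How many participants would be incomplete?** If each value is missing independently with probability m, the expected number is 10 x (1 - (1 - m)^k):

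| m | k = 3 | k = 5 | k = 7 |
|---|---|---|---|
| 1% | 0.3 | 0.5 | 0.7 |
| 5% | 1.4 | 2.3 | 3.0 |
| 10% | 2.7 | 4.1 | 5.2 |

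Withdrawal instead clusters missing values in a few people. If each person who withdraws loses between 1 and k - 1 conditions with equal probability, the average loss is k/2, or half that person's values. Then 5% of all values missing means 10% of people incomplete (9.0 of 10 complete), and 10% missing means 20% incomplete (8.0 complete). The scattered pattern would leave 7.7 or 7.0 complete at 5%, and 5.9 or 4.8 at 10% (k = 5 or 7). Clustering fits Section 3 better and is used for the main figures.

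**Step 2. Power with complete rows only.** For n complete participants the F test has k - 1 and (n - 1)(k - 1) degrees of freedom and noncentrality n x 1.25² x (k - 1)/k, which is 1.25n for k = 5 and 1.34n for k = 7.

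| Complete participants | k = 5 | k = 7 |
|---|---|---|
| 10 | 76.1% | 73.6% |
| 9 | 70.2% | 67.5% |
| 8 | 63.3% | 60.4% |
| 7 | 55.4% | 52.6% |

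**Step 3. Complete rows against all available data.** This simulation uses clustered withdrawal, with the number incomplete varying around its mean (k = 5 and 7):

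| Mean incomplete of 10 | Complete cases | All available data |
|---|---|---|
| 1 | 68% | 70-71% |
| 2 | 61% | 67-68% |
| 3 | 52-54% | 62-63% |

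Type I error with all available data was 4.1-5.4%. A repeat with other random draws agreed to within about 3 percentage points.

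**Step 4. Is anything lost when data are complete?** With one value per participant and estimator, participant as a fixed effect gives the planned F exactly. With participant random (REML, n = 10, k = 3, 5 and 7), F agreed to a relative difference below 1e-7 whenever the participant variance estimate was positive. That was at least 497 of 500 data sets when participant and residual SDs were equal. When the estimate was truncated at zero, F differed by up to 37%.

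**Step 5. What if rows are kept separately by speed profile?** Settings: complete data, two profiles per estimator, n = 10, k = 5 or 7, participant and residual SD 1, no true estimator effect. A model whose only random effect is participant then has type I error of 10-11% if the participant-by-estimator SD is 0.5, and 21-24% if it is 1.0. The ANOVA on participant-by-estimator means stays at about 5%.

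**The case against.** The strongest case against is that the loss is hypothetical. No dropout or missing-value rate is given, Section 1 describes ten people who complete, Section 2 aims for 10-15, and Section 3 offers a return visit. At a 1% miss rate the expected loss is under one person. This stands as to size: a reader might infer that two or three of ten will be lost, and the documents do not support that. It does not remove the gap, because a recruitment target does not say how a partial record is analysed.

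Second, dropping people is a software default and not plan text. A reader might infer that the plan prescribes discarding them; it does not. A long-format ANOVA with participant as a factor also keeps them, with nearly the same power as the mixed model (75.4% for both with k = 5, one condition missing in each of three people, and an effect scaled to 80% power with ten complete). That is one of the two versions accepted in the fix, and the plan should name which it uses.

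Third, a reader might want profile and visit terms in the model. The documents do not support this. Section 3 uses P1, P2 and OVG to name where a model was adapted; it does not say that every estimator is tested under both profiles. If each runs only in its own setting, profile is confounded with estimator. If they are fully crossed, averaging already removes the profile main effect. Section 3 also opens by calling this a single-visit study.

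Fourth, all-available data do not cure selection if discomfort itself drives the gaps in a way the observed values do not capture. This stands. Nor does the point carry over in the same way to the paired t-tests, which lose only people missing one of the two values compared.

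**Conclusion.** The point holds as a gap in the analysis plan with a modest, conditional cost. The complete-row form gives up about 2-3 percentage points of power if one of ten participants is incomplete on average, 6-7 points if two are, and 8-11 points if three are. These figures rest on an assumed 1.25 SD effect, 5 to 7 estimators, sphericity and clustered withdrawal. None of these comes from the documents, and with no incomplete participants the cost is zero.

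Much larger losses appear only if missing values are scattered independently across people, which is not the mechanism Section 3 describes. It would also go too far to say that any mixed model gives the same answer as the planned test. The equivalence needs one value per participant and estimator, a compound-symmetric structure, no sphericity correction and, with participant random, a positive variance estimate.

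**What to change.** Amend Section 4 as follows:

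1. List the estimators in the real-time analysis. Reduce the data to one error value per participant and estimator, averaged over the same test conditions for every estimator.
2. Fit a linear model with estimator as a fixed effect and participant as a random or fixed effect, using Kenward-Roger degrees of freedom if random. Keep every participant with at least two estimators, and take the estimator comparisons from this model.
3. If rows are kept by test profile, add a participant-by-estimator random effect. Do not add profile or visit terms unless estimators are crossed with them.
4. Record the reason for each missing condition, and report the complete-case ANOVA as a sensitivity analysis.

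The cost is a few sentences of plan text and slightly more analysis work, with no new measurements beyond logging reasons. The downside is reliance on missing at random, which item 4 helps a reader to judge but cannot verify.

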#### **5. Research Risks**

The main risk of the study is a possible fall. Each participant will be given ample time to get accustomed to using the devices. This adjustment period will involve getting used to balancing with the given device or control method. In this adjustment period, participants run the highest risk of falling. However, to manage this risk, there will be rails around the treadmill at all times, which the user may hold to prevent falls. Based on the participant's comfort, there are varying levels of additional treadmill support or padding. After the adjustment period, if the participant is comfortable enough for freestanding walking there will be spotters next to them at all times. When testing the prosthetic, there is an additional risk of irritation caused by the method of attachment. The level of risk varies depending on the walking style and skin sensitivity of the participant. To reduce the likelihood of irritation, amputees will use their own prosthetic socket and non-amputees will use a commercial assistive walking device. The instruction manual for the commercialized assistive walking device (iWALK) is attached as a separate document.

Participants are strongly encouraged to vocalize any discomfort to try and prevent irritation from occurring. If irritation does occur, brief medical care in the form of disinfectant wipes and/or a Band-Aid will be provided. In the unlikely event of an irritation too severe for a Band-Aid, the participant will be referred to a physician. Any adverse events will be reported to ORIA within the regulated time frame. If the metabolic system is used by the participant, there are slight risks associated with the system. They include transmission of communicable diseases, aspiration of contaminants, irritation from wear, choking/strangulation, and discomfort. To protect against infection, the mask and monitor will be properly disinfected between uses, and will always be handled with disposable

sanitary gloves. Also, antibacterial filters will always be used with the metabolic mask to prevent aspiration of contaminants.

To prevent irritation subjects are strongly encouraged to notify a researcher if they feel pain or discomfort. Careful attention will be paid to the position of the chords, to avoid entanglement and possible choking or strangulation. Verbal communication is strongly encouraged throughout testing to act as a preventative measure for discomfort. General risks associated with testing any electrical device include fire and electrical shock. These risks will be avoided by keeping the device away from water or open flame sources. Researchers will always be vigilant about the conditions of the testing environment.

General risks associated with testing any electrical device include fire and electrical shock. These risks will be avoided by keeping the device away from water or open flame sources. Researchers will always be vigilant about the conditions of the testing environment. No undue psychological risks are anticipated during this study, and volunteers retain the ability to stop testing at any point. Privacy will be maintained during testing via an enclosed indoor testing environment by monitoring the perimeter for unauthorized personal; no significant privacy risks are anticipated.

## **6. Confidentiality**

Participants will sign a consent form before participating which explains that no identifiers linking them to this study will be included in any sort of report that might be published except for the video taken. Participant faces will be blocked out upon request. They will be given a pseudonym different from their own name that will be referred to in studies published, if at all. Participants will be assured in the informed consent that the data will be used only for studies that are consistent with the original research purpose.

This consent form will be filed securely in an official area. People who have access to information include the Principal Investigators and research study personnel. Representatives of regulatory agencies such as the Office of Human Research Protections (OHRP), the Food and Drug Administration, the DoD, and entities such as the Georgia Tech Office of Research Integrity Assurance may access participant records to make sure the study is being run correctly and that information is collected properly.

Information about participants related to this study will be kept confidential to the extent permitted or required by law.

When the data is stored, it will no longer be linked to the subject's personal information. There will be a master list stored separately that connects the subject identifiers with their personal information, for when they need to be contacted. The data will be kept on the computers of the research personnel only. These computers will all be password protected to prevent nonauthorized access to the data. Data will be transmitted electronically between researchers. The master list of subjects and their personal information will not be transmitted in any form between researchers. This master list will only be in the possession of the PI and researcher responsible for recruiting. It will not be shared with anyone else in any way.

## **7. Benefits**

The goal of this research is to improve upon the existing design processes of prostheses and exoskeletons for the future, and there are no foreseen direct benefits from this study. Participation in these tests may help any person that may someday need or want one of these devices. These tests will not benefit participants personally unless they intend to use these types of devices in the future.

